8 TIMING OF ANALYSES

8.1 Interim Analysis

No interim analyses are planned for this study.

8.2 Final Analyses and Reporting

All planned analyses described in the SAP will be performed after the study has completed, all outstanding queries resolved, and the database has been locked.

9 STATISTICAL METHODS

9.1 General Statistical Consideration

Statistical analyses will be reported with tables, figures, and listings, presented in rich text format, and using recommended ICH numbering. Output specifications for all tables, figures, and listings will be in conformance with guidelines specified by the [ICH of the Electronic Common Technical Document Specification](#) (Apr 2003).

All summaries will be presented by assigned treatment group, or actual treatment group where applicable. In addition, data will be tabulated for all patients combined. All relevant data collected on the electronic case report form (eCRF) will be presented in by-patient data listings, to include the site identifier, patient number, and assigned treatment group.

In general, continuous variables will be summarized by the number of patients with non-missing data, mean, SD, median, 25th percentile, 75th percentile, minimum, and maximum values. Categorical variables will be summarized by the number and percentage of patients in each category.

9.2 Patient Disposition

Screen failure information is collected in an interactive web response system (IWRS), not on the eCRF and it is not be incorporated into the Study Data Tabulation Model (SDTM) database. Information on participant screening will be presented in terms of the overall number of participants screened, number of patients who are screen failures, reasons for screen failures, and the number of participants in screening.

Participant disposition will show the number of patients who have been enrolled, in each analysis population, took study drug, discontinued treatment, discontinued from the study, reasons for discontinuations, completed 12 weeks of study treatment, completed the study, and completed the follow-up study visit.

Completion of the follow-up study visit is defined as completing the date of visit eCRF for the follow-up visit.

9.3 Protocol Deviations

Protocol deviations will be categorized as important or other according to the protocol deviation specification document. A by-patient listing of important protocol deviations will be provided for the ITT population.

Patient eligibility including inclusion and exclusion criteria that were not met at randomization will be listed for all patients in the ITT population.

9.4 Demographic and Baseline Characteristics

The following demographic characteristics will be presented for the Safety population in listing, and summarized by treatment and overall:

- Age at informed consent (continuous and categorical variable: < 30, 30-50, and > 50 years) will be summarized
- Sex
- Of childbearing potential (Yes/No)
- Ethnicity
- Race
- Height
- Weight
- Body mass index (BMI) (continuous and categorical variable: obesity class 1 (30-34.9 kg/m²), obesity class 2 (35-39.9 kg/m²), extreme obesity class 3 (≥ 40 kg/m²))
- Alcohol Use Disorders Identification Test (AUDIT) score

BMI will be calculated as: weight (kg) / [height (cm) / 100]². The imputation rules for missing or partial diagnosis dates are described in [Section 12.1](#).

9.5 Medical History

Medical history will be summarized for all patients in the Safety population. Frequency counts and percentages to summarize patients reporting medical history by system organ class and preferred term (coded using MedDRA version 23.0 or above) will be presented.

9.6 Prior and Concomitant Medications and Subsequent Therapies

Medications will be coded using the WHO Drug Global B3 version September 2019 or above. Medications entered on the eCRF will be mapped to ATC drug class (level 4) and generic drug name.

A prior medication is defined as any medication administered prior to the date of the first dose of study drug. A concomitant medication is defined as any medication administered on or after the date of the first dose of study drug and up to and including the last dose date. Medications newly administered after the last dose date are defined as subsequent therapies. A medication may be defined as more than one medication classification (prior, concomitant, or subsequent). The imputation rules for missing start and end date of a concomitant medication are described in [Section 12.1](#).

The proportion of patients who received prior, concomitant, and subsequent therapies or medications will be summarized separately for the Safety population. For all table summaries, the number and percentage of patients receiving any medication will be summarized by treatment group and overall. The preferred drug name and the preferred drug name within ATC drug class will be summarized separately and displayed by alphabetical order of ATC and descending order of incidence for the preferred drug name. Patients reporting use of more than one medication at each level of summarization (any medication received, ATC class, and preferred drug name) will be counted only once. The medication classification (e.g., prior, concomitant, subsequent, or a combination of classification) will be presented on the listing of prior, concomitant, and subsequent medications.

9.7 Extent of Exposure and Study Drug Compliance

All recorded information on oral dosing of miricorilant, including kit number, actual dose, start and end date, any dose modifications and related reason will be presented in a data listing sorted by start date of administration.

A table by treatment arm and overall will provide summary statistics on the following:

- Duration of Exposure: The duration of exposure for each study drug will be presented in days and calculated as:

$$\text{Duration} = \text{Expected date of last dose} - \text{Date of the first dose} + 1.$$

Expected date of last dose will be the latest of either the last dose date or the last missed dose date.

- Total Tablets Received: The total dose received for each study drug will be:

$$\text{Total Tablets Received} = \text{Total tablets dispensed} - \text{Total tablets returned}.$$

- Total Tablets Expected: A patient will have an expected number of tablets determined by the earliest start date and the latest end date times six tablets taken daily. For patients where their tablets received is either zero or missing, an associated expected number of tablets is included in the total tablets expected derivation. Therefore, the total tablets expected to be taken is:

$$\text{Total Tablets Expected} = \text{Duration of Exposure} \times 6.$$

- Compliance: Compliance is calculated for each study drug as:

$$\text{Compliance} = (\text{Total Tablets Received} / \text{Total Tablets Expected}) \times 100.$$

A by-patient listing including the study drug start date, study drug end date, duration, number of pills taken, number of pills expected to be taken, and overall compliance will be produced.

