3.4.3 End of Treatment

The end of treatment is defined as the date on which the patient received his or her last treatment, which may be the end of the Treatment Period if the patient completed all treatments or may be earlier if the patient discontinued study treatment before the designated stopping point.

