Elevations of ALT or AST are defined as a baseline ALT or AST $<ULN$ that increased to $>3\times ULN$ on treatment, or a baseline ALT or AST $>ULN$ and on-treatment $>2\times$ baseline. Elevations should be confirmed with repeat testing within 48 to 72 hours. If confirmed, and if no other cause of laboratory abnormality is immediately apparent, the Corcept Medical Monitor is to be notified. Patients with ALT or AST elevations must be placed into close observation (see [Table 2](#)).

Table 2 Criteria for Dose Modification or Discontinuation Due to Special Safety Events

Safety Event	Criteria for Interrupting and Restarting Study Treatment and Patient Management	Criteria for Stopping Study Treatment
Excessive GR or MR antagonism	
Criteria: signs and symptoms of excessive GR and MR antagonism (Section 1.5)
 
Management:
 
 • Immediately interrupt miricorilant treatment for ≥ 5 days and start standard supportive care, including intravenous fluids as indicated. • If appropriate, administer supplemental glucocorticoids given in high doses to overcome the GR antagonism produced by miricorilant. Initially, consider intravenous hydrocortisone, followed by additional intravenous or oral doses once or twice daily for 1 to 3 days and tapered thereafter, depending on clinical response. In some cases, higher doses of hydrocortisone for longer periods of time may be required. • If the patient has been receiving treatment with an MR antagonist, consider discontinuing it, particularly in the presence of hypotension. • Restart miricorilant treatment only if the workup reveals an alternative cause for symptoms of possible excessive GR/MR antagonism and after consultation with the Corcept Medical Monitor. 	
A combination of the following Grade 3 or higher events: fatigue, anorexia, nausea, and vomiting (associated with decreased oral intake), and abdominal pain.

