5.8 Study Drug Accountability and Treatment Adherence

Study drug adherence will be determined by review of the patient dose diary and counting returned tablets. On visit days, study drug should be taken in the clinic during the visit and after initial blood draws.

A patient who is assigned a study drug (i.e., to 600 mg miricorilant, 900 mg miricorilant or placebo, for 12 weeks of treatment) will be considered nonadherent if he or she misses >20% of the prescribed doses during the study, unless the patient's study drug was withheld by the Investigator for safety reasons. Similarly, a patient will be considered nonadherent if he or she is judged by the Investigator to have intentionally or repeatedly taken more than the prescribed amount of study drug. Patients found to be nonadherent with their assigned treatment regimen

should be assessed to determine the reason for nonadherence and educated and/or managed as deemed appropriate by the Investigator to improve adherence.

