7.1 Definitions

Study day for efficacy will be calculated in reference to the date of first dose of miricorilant or placebo (Study Day 1). For assessments conducted on or after the first dose date, study day is calculated as (assessment date – first dose date + 1). For assessments conducted before the first dose date, study day is calculated as (assessment date – first dose date). There is no study Day 0.

Treatment-emergent period: The treatment-emergent period is defined as the period of time from the date of the first dose of study drug (inclusive) through 28 days after the last dose of study drug. The treatment-emergent period will be used in the summaries of TEAEs.

Baseline will be the assessment on the Day 1 visit if non-missing, or the last non-missing assessment prior to first dose of study drug if Day 1 visit is missing.

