7.6 Analysis Visit Windows

In analysis of data summarized by study visit, unscheduled and early termination visits will be reassigned a study visit where data is scheduled for collection based on the actual days relative to the date of first dose ([Table 1](#)). If multiple visits fall in the analysis visit window, the one closest to the target day will be used. If two visits are equidistant to the target day, then the later visit will be used.

Table 1 Analysis Visit Windows for Assessments

Visit Name	Start Day	Target Day	End Day
Baseline	—	1	—
Week 2	2	15	22
Week 4	23	29	36
Week 6	37	43	50
Week 8	51	57	64
Week 10	65	71	78
Week 12	79	85	92
Follow-up	> Study day of last dose of study drug	Initial visit after end of treatment	
Additional Follow-up	> Study day of last dose of study drug	Second visit after end of treatment	

Note: Any unscheduled and early termination visits that occur after the last dose of study drug will be classified in the follow-up period.

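### SAP 9.7 counts days up to the last missed dose as exposure, because one variable serves as both exposure duration and the basis for tablets expected

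*SAP*

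**What the plan says.** SAP 9.7 defines Duration of Exposure as the expected date of last dose minus the date of first dose, plus 1. On the end point it says: "Expected date of last dose will be the latest of either the last dose date or the last missed dose date". Total tablets expected is this duration times 6. Compliance is tablets received (dispensed minus returned) divided by tablets expected, times 100. No separate duration to the last dose taken is defined.

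Other sections use the last dose itself:

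- Protocol 3.4.3: "The end of treatment is defined as the date on which the patient received his or her last treatment".
- SAP 7.1, treatment-emergent period: "from the date of the first dose of study drug (inclusive) through 28 days after the last dose of study drug".
- SAP 7.6, note to Table 1: "Any unscheduled and early termination visits that occur after the last dose of study drug will be classified in the follow-up period".
- SAP 9.6: "Medications newly administered after the last dose date are defined as subsequent therapies".

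SAP 10, which lists the changes from the protocol, does not mention the exposure definition.

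**The concern.** A missed dose is not exposure. The rule in 9.7 makes a difference only when the last missed dose falls after the last dose taken, and then it adds days without drug to the reported duration. The same calendar day can be exposure in 9.7 and post-treatment in 7.6 and 9.6.

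The situation is plausible. Protocol Table 2 says, for suspected excessive receptor antagonism, "Immediately interrupt miricorilant treatment for ≥ 5 days", and it allows a restart only under conditions. An interruption that never restarts, or is still open when the study stops, leaves days after the last dose, and some may be recorded as missed.

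At stake is a descriptive safety number. SAP 9.8 says that the study was terminated over safety observations and that no patient reached Week 12. Time on drug is basic context for the adverse event tables, and when durations are short each added day is a larger share of the total.

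**Working it through.** The plan states no exposure or compliance figure, so there is none to reproduce. The check applies the formulas in 9.7.

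**Inputs from SAP 9.7:** the end-date rule, the duration formula, six tablets a day, and compliance as received over expected.

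**Assumed inputs (not in the documents):** first dose on Day 1; last dose on Day L; last recorded missed dose m days later (m = 0 means none); every dose through Day L taken and all unused tablets returned.

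**Formulas**

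- Duration under 9.7 = (L + m) − 1 + 1 = L + m
- Duration to last dose taken = L
- Overstatement = (L + m)/L − 1
- Compliance under 9.7 = 6L / [6(L + m)]

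**Last dose on Day 30**

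| m | Duration under 9.7 | Overstatement | Compliance under 9.7 |
|---|---|---|---|
| 0 | 30 | 30/30 − 1 = 0 | 180/180 = 100% |
| 1 | 31 | 31/30 − 1 = 3.3% | 180/186 = 96.8% |
| 5 | 35 | 35/30 − 1 = 16.7% | 180/210 = 85.7% |

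**Wider range of assumed timelines**

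| L | m = 7 | m = 14 |
|---|---|---|
| 28 | 35 days (+25.0%) | 42 days (+50.0%) |
| 42 | 49 days (+16.7%) | 56 days (+33.3%) |
| 56 | 63 days (+12.5%) | 70 days (+25.0%) |

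**One day under each section.** Take L = 30, m = 5 and look at Day 33. Under 9.7 it lies inside Days 1 to 35, so it is exposure. A medication first given that day is a subsequent therapy under 9.6. An early termination visit that day is follow-up under 7.6. An adverse event with onset that day is treatment-emergent, because 7.1 runs to Day 30 + 28 = Day 58. That limit uses the actual last dose, so the rule in 9.7 does not move it.

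**Missed doses before the last dose.** Take L = 42 with seven missed days inside the interval. Duration is 42 days whether it ends by the 9.7 rule or at the last dose, and compliance is (42 − 7) × 6 / (42 × 6) = 210/252 = 83.3% either way. The end-date rule has no bearing on interior gaps.

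**After the change.** With L = 30 and m = 5, exposure becomes 30 days. The expected dosing period stays at 35 days and compliance at 180/210 = 85.7%. Had the denominator also been cut at the last dose, compliance would be 180/180 = 100% and the five missed doses would vanish from it. Two quantities are therefore needed.

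**The case against.** The strongest reply is that 9.7 is open about what it does. It calls its end point an expected date, states the rule, and uses it for compliance, where running through missed doses is right. Sections 7.1, 7.6 and 9.6 classify events, visits and medications; none of them defines exposure. All of that stands, and it narrows the fault to one thing: an expected-dosing interval is also labelled and reported as exposure.

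It is also fair that the effect is conditional. Whether days after a permanent stop are recorded as missed depends on data-collection conventions that the documents do not give. Much can be recovered from the listings in 9.7, which show dosing dates, modifications and reasons by patient. That limits the harm but does not correct the summary table.

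A reader might infer further that compliance is wrong because safety holds followed by a restart lower it, contrary to Protocol 5.8, which makes an exception where "study drug was withheld by the Investigator for safety reasons". The documents do not support this. Protocol 5.8 is a conduct rule with its own cut-off (more than 20% of doses missed) for deciding when a patient is nonadherent. SAP 9.7 computes a tablet percentage and applies no cut-off. Such holds lie inside the first-to-last-dose interval, so their effect does not come from the end-date rule and would not change if exposure ended at the last dose.

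**Conclusion.** The definition is wrong as written for exposure and sound for compliance. The point is minor. The overstatement equals the number of days from the last dose to the last recorded missed dose: 0, 1 or 5 days (0, 3.3% or 16.7%) in the Day 30 illustration. All timelines are assumed.

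It would go too far to conclude that exposure was in fact overstated in this trial, since the documents give no count of trailing missed doses and it may be zero. Nor does the rule alter any safety classification: the treatment-emergent period is tied to the last dose, and no population or test uses the 9.7 duration. The effect is confined to descriptive exposure output. The duration on study drug in the complete-resolution listing (SAP 9.8.3.2) would share it only if programmed from 9.7; the SAP does not say.

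**What to change.** In SAP 9.7:

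1. Define Duration of Exposure as the date of the last dose actually taken minus the date of the first dose, plus 1.
2. Keep the present interval, through the last missed dose, under a separate name such as expected dosing period, and set total tablets expected to that period times 6. Trailing missed doses then still lower compliance.

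The cost is SAP wording and one derived variable, from dates that the present rule already needs. The new exposure duration still contains any days without drug between the first and last dose, so it is elapsed time from first to last dose and not a count of dosing days.

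Two clarifications are optional and not part of the error: stating whether a dose withheld by the Investigator is recorded as missed, and showing compliance with and without safety-withheld days.

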5.5 Method of Study Drug Assignment and Randomization

All patients will be randomly assigned to the study drug (one of the 3 treatment groups) using a centralized interactive web response system (IWRS). Subject unique identifier creation and treatment allocation will be performed using the system. Randomization will be stratified by diabetes status to ensure that there will be an equal number of patients with diabetes in each treatment group. Before the study is initiated, the log-in information and directions for the IWRS will be provided to each site.

Study drug will be dispensed at the study visits summarized in the SoA ([Appendix A](#)).

Returned study drug should not be re-dispensed to the patients. However, study treatment brought back by the patient for accounting reasons can be returned to the patient.

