11.7 Drug Accountability

It is the responsibility of the Investigator to maintain drug accountability at the study site and ensure that a current record of study-drug disposition is maintained. This includes acknowledgment of receipt of each shipment of study product (quantity and condition), patient dispensing records, and returned, lost, or accidentally or deliberately destroyed study product.

Dispensing records will document quantities received from the Sponsor (or designee) and quantities dispensed to patients, including lot number, date dispensed, patient identifier number, patient initials, the initials of the person dispensing the drug, quantities of drug returned by the patients and disposal/return of returned study drug. Prior to destruction of returned study drug, the study monitor should confirm drug accountability, if allowed by local institutional policy.

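### SAP 9.7 counts every tablet not returned as taken, so Total Tablets Received and Compliance can be overstated, even above 100%

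*SAP*

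**What the plan says.** SAP 9.7 builds its exposure table from four quantities.

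- **Duration of Exposure** comes from dates: "Expected date of last dose will be the latest of either the last dose date or the last missed dose date".
- **Total Tablets Expected** is that duration times six: "A patient will have an expected number of tablets determined by the earliest start date and the latest end date times six tablets taken daily".
- **Total Tablets Received** is introduced by "Total Tablets Received: The total dose received for each study drug will be", followed by tablets dispensed less tablets returned.
- **Compliance** is received over expected, times 100.

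For the by-patient listing, the section says that study drug dates, duration, "number of pills taken, number of pills expected to be taken, and overall compliance will be produced". It gives no separate derivation of pills taken. For patients whose tablets received are zero or missing it keeps the expected tablets in the denominator. It says nothing about losses, unreturned supplies or values above 100%, and it does not mention the diary.

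The protocol describes more sources. Section 5.8 states: "Study drug adherence will be determined by review of the patient dose diary and counting returned tablets". Under Section 5.7 the diary holds the tablet number, date and time of each dose, and patients are told to bring back all unused drug. Section 11.7 has the site keep records that cover "returned, lost, or accidentally or deliberately destroyed study product". Section 7.3 has unused drug recorded at each treatment visit. Section 5.5 bars re-dispensing of returned drug, but adds that "study treatment brought back by the patient for accounting reasons can be returned to the patient".

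**The concern.** Dispensed minus returned equals intake only if every unused tablet comes back and is counted once. Otherwise the difference mixes tablets swallowed with tablets lost, destroyed or left at home. The SAP labels the result as dose received and uses it as pills taken, while two records that could separate these components (the site's loss record and the diary) play no part in the formula.

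The setting makes this more than a formality. SAP 9.8 says that the sponsor ended the study early for safety and that no patient reached Week 12, so part-used last supplies are plausible. SAP Section 10 removes the PK analysis and leaves PK data as listings. Tablet count and duration are then the main summarized measures of exposure beside the safety tables.

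**Working it through.** The documents give no numerical compliance figure, so there is nothing to reproduce. The check applies the SAP formula to illustrative patients.

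**Inputs from the documents.** Six tablets a day in every arm (Protocol 5.1.2); 42 tablets per card (Protocol Table 1); dispensing on Day 1 and every two weeks to Week 10 (Protocol Appendix A); nonadherence means more than 20% of prescribed doses missed (Protocol 5.8).

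**Assumptions.** Where stated, 84 tablets per dispensing (6 × 14). Quantities lost, unreturned or handed back are chosen for illustration. A supply never brought back enters as zero returned; the SAP does not say whether it would instead be set to missing.

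**Formula.** Compliance = 100 × (dispensed − returned) / (6 × days). Each tablet neither taken nor returned adds 100/(6 × days) points. Over 28 days that is 100/168 = 0.595 points.

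1. *Last supply not returned.* Dispensed on Days 1, 15 and 29: 3 × 84 = 252. Last dose on Day 31: expected 31 × 6 = 186. Nothing returned: 252/186 = 135%. At full adherence 186 tablets were taken, so 252 − 186 = 66 are unaccounted for. Had they come back, the result would be 186/186 = 100%.
2. *One card lost over 42 days.* Dispensed 252, expected 42 × 6 = 252, returned 0: computed 100%. True intake is 210/252 = 83.3%, so 16.7% was missed.
3. *Losses over 28 days.* Dispensed 168, expected 168, returned 0: computed 100% whatever the loss. True values:

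| Tablets lost | True compliance |
|---|---|
| 6 | 162/168 = 96.4% |
| 24 | 144/168 = 85.7% |
| 34 | 134/168 = 79.8% |
| 42 | 126/168 = 75.0% |

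At 34 tablets the missed share is 34/168 = 20.2%, just past the protocol's limit. The limit is in doses; in whole daily doses it takes six, or 36 tablets (36/168 = 21.4%).

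4. *Tablets handed back.* Dispensed 126 on Day 1 and 84 at Week 2, total 210. All 168 due tablets are taken. The patient brings 42 to Week 2, gets them back, and has 42 left at Week 4. The result depends on the recording:
   - both counts summed as returns: (210 − 84)/168 = 75%
   - only the final return counted: (210 − 42)/168 = 100%
   - hand-back also logged as dispensed: (252 − 84)/168 = 100%

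5. *Date-based quantities.* Duration of Exposure and Total Tablets Expected contain no tablet count, so their error is zero in every case.

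**The case against.** Dispensed minus returned is a conventional pill count, and it is right when patients do as Protocol 5.7 asks. Unused drug is recorded at treatment visits, and the Early Termination and Follow-Up visits include the same procedures. A value such as 135% would stand out in the by-patient listing. No analysis population depends on compliance, treatment-emergence is set by dose dates, and SAP 9.9 makes no between-group safety comparisons. Protocol 5.8 is also not part of the protocol's statistical section, so its absence from SAP Section 10 is arguable. All of this limits the impact. It does not repair the rule: a lost card that turns 83% into 100% shows nothing unusual in a listing.

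A reader might infer four stronger things, which the documents do not support.

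- *That the formula is wrong in both directions.* The downward error needs interim counts summed as returns with no offsetting dispense entry. No text says so, and Protocol 5.5 can be read as separating returned drug from drug brought in for counting. What is shown is that returned is undefined.
- *That all exposure measures are affected.* The date-based ones are not.
- *That nonadherence will be misclassified.* The Day 31 patient may have missed nothing and the 42-day patient missed 16.7%; neither crosses the limit. The 28-day case shows that a breach can be hidden, but SAP 9.7 applies no 20% classification. Protocol 5.8 uses the limit to prompt assessment and education at the site.
- *That unreturned supplies were common because the trial stopped.* The documents give no stop dates and no return counts.

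**Conclusion.** The upward error follows directly from the formula in SAP 9.7: tablets lost, destroyed or never returned are counted as taken. Total Tablets Received, the listed pills taken and Compliance can all be too high. The illustrations give an excess of about 17 points for one lost card over 42 days, 25 points for the same card over 28 days, and an impossible 135% for a Day 31 stop with the last supply kept. The first and third rest on the assumed 84 tablets per dispensing, and all rest on assumed losses or non-return; the number of patients affected is unknown. The downward error from handed-back tablets is possible but not established. The consequence is modest, because these outputs are descriptive and feed no other analysis, but the section should still be corrected.

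**What to change.** In SAP 9.7:

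- Define tablets taken as dispensed, minus final net returns (excluding tablets handed back to the patient), minus tablets recorded as lost or destroyed. Use this for Total Tablets Received, pills taken and Compliance.
- Where a patient's last supply was not returned, use the diary tablet count if it is in the database. Otherwise report compliance as not evaluable for that interval, with the number of patients affected.
- Flag values above 100% in the table and listing.

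In SAP Section 10, if the diary is not used, state that adherence departs from the protocol's diary-plus-count method.

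The cost is a few lines of SAP text and a little programming, and some intervals will be reported as not evaluable. One condition must be checked first. Protocol Appendix A has the diary assessed and handed back to the patient, and Section 11.7 describes records kept at the site. Neither document says that diary tablet counts or losses reach the analysis database, so loss entries may have to be transferred from the site records.
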